D. Treatment of Iatrogenic Weight Gain and Obesity in Psychotic Patients: Because the literature thus far suggests that some of the SGAs cause somewhat less weight gain than others—one suggested strategy is to attempt weight loss by simply switching patients from CLOZ or OLZ (SGAs associated with the most weight gain) to ARI, ZIP, RIS or QUE (11, 23). While there is some evidence that RIS is useful in treatment refractory patients, (i.e., patients who take CLOZ) (11) no such data exists yet for QUE although Reinstein's work is somewhat promising (24). The problem is that one cannot assume equal antipsychotic efficacy in every patient for each antipsychotic medication. Indeed, CLOZ is reserved for the most refractory patients and no other medication to date has proven as effective in such patients. Thus, switching medication for weight loss purposes alone must be done with great caution due to the risk of psychotic exacerbation, rehospitalization, and even death. Ideally, clinicians will try to choose the medications that are most favorable and least harmful in terms of weight gain, but we are often limited by formulary and other financial restrictions.

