Behavioral interventions such as calorie restriction, exercise, and behavior modification are key elements to successful, sustained weight loss. Three behavior modification techniques will be key elements in the Lifestyle Balance Program: (1) motivational interviewing and (2) contingency contracting, and (3) social skills training provided by the Lifestyle Balance coaches. These will be described in the Methods section below. In fact, behavioral interventions have been used successfully to prevent diabetes and demonstrated efficacy equal to the anti-diabetic medication metformin (43). Behavioral interventions may be an excellent option for the SMI population given the relative risks of any of the above strategies discussed — switching antipsychotics to a potentially ineffective one, adding medications with additional toxicities and propensities to worsen psychiatric symptoms, and finally surgery that is risky in patients whom surgeons feel will not benefit from such intervention. Most publications on weight loss in the SMI population to date are neither controlled nor large, but offer some hope that behavioral strategies can be of assistance to patients with psychotic disorders. In one small 14-week study, (N=14) patients achieved, on average, 10 pounds of weight loss when given behavioral interventions (classes and a contingency model—rewards for weight lost) compared to a control group (44). Retrospective analysis of simple interventions we have offered in clinic suggest behavioral interventions such as simply weighing patients, meeting with a nutritionist, maintaining a food diary, and encouraging exercise were fairly successful in RIS and OLZ treated subjects, although these strategies seemed to have little effect in CLOZ treated subjects (11).

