1. Demographics: This Merit Review Grant was funded in June of 2006 at which point only 35% of the funds for the year were provided. We have screened 225 veterans to participate and 123 have been randomized. 113 were male and 10 were female. Of the 123 patients randomized, 78 of them are currently active participants or have finished the program. Of these 78 participants, 36 (29%) are African-American, 2 (1.6%) are Asian-American, 30 (25%) are Caucasian, 6 (5%) are Hispanic, and 4 (3%) identify as mixed or other ethnicity. In addition to severe mental illness, over 50% had substance abuse problems. To date (April 2009) there are still 18 active patients in the protocol. The current cohort of patients will not be completed with their full yearlong participation in the study until September of 2009.

The purpose of this study was to test a modified version of the multi-modal Diabetes Prevention Program which includes the Lifestyle Balance classes, exercise, and individual coaching over a one-year period of time in severely mentally ill patients who had antipsychotic associated obesity.

2. Preliminary Results:

a) *Weight Loss Findings:* Preliminary data analysis using a mixed model analysis on the basis of the current status of the patient cohort (at this point data for 46 participants who have completed 6 or more months, 22 of them have completed 1 year) shows that we can expect a difference of 11.8 pounds between

the lifestyle balance group and the standard treatment group, with a weight loss of 6.6 pounds for the lifestyle balance group, and a gain of 5.2 pounds for the standard treatment group ($F(1,935)=25.1, p<.001$). This is more than twice the group difference we predicted in the original proposal (5.5 pounds). Our poster presentation in 2007 demonstrated that 37% of our patients enrolled in the active treatment arm of the study had lost 5 or more pounds compared to 0% of patients in the control group (usual psychiatric care). This preliminary data has also been submitted for poster presentations at the World Psychiatric Association to be presented in Italy in April 2008, as well as the international Congress on Schizophrenia Research in April of 2008. Range of weight loss for the first 6 months was from a loss of 50- pounds to a gain of 14 pounds for the intervention group and from a loss of 19 pounds to a gain of 29 for the usual care group.

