g) *Impact of Particular Medication on Success of Weight Loss Intervention*: Preliminary analyses of the data from our current Merit Review Study, using a mixed general linear model shows that there are significant differences in the degree to which patients on different medications profit from our Lifestyle Balance Program ($F(5,7220)=15.06, p<.01$): patients on quetiapine, olanzapine and fluphenazine profit from the program, while the weight gain in patients on clozapine and risperidone does not appear to respond to the training program. These results are very preliminary due to the small number of patients in each of these patient subgroups at the moment.

h) *Impact of a Multi-Modal Approach*: The preliminary data analyses suggest that this intervention has an effect beyond what a pure exercise program can provide. Patients who reported at the baseline measurement that they were already exercising showed the same effect of the intervention as patients who had reported that they were not exercising (Test for the difference between these groups: $F(1,862)=0.03, p=.86$) (56).

3. Preliminary Conclusions from the Current Study: Though our study is not complete, we have excellent interim data that demonstrates that the Lifestyles Balance program, adopted from the DPP and administered for a year has positive impact. Even in the preliminary sample, we show significant positive impact on measures of the patients' weight, BMI, metabolic syndrome, and measures of cardiovascular disease risk factors. Other, more nuanced measures of physical and mental health also show sizable positive changes; these changes are not large enough to be detected in the preliminary, but the final sample as projected will provide sufficient power for them. We believe these changes in a population challenged with severe mental illness (and a significant proportion with a history of substance abuse) are quite encouraging.

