3. Repeated measures analyses: We propose to longitudinal (repeated measures) analyses to maximize the additional power we gain by observing the same subjects across 12 months.. Repeated measures analyses permit contrasts at each time point, and also describe and compare trajectories of change (trends), speed and durability of effects. We will also conduct separate cross-sectional to provide outcome data for ongoing safety review, interim progress reports, study oversight and conduct.

The primary design for longitudinal (repeated measures) analyses of continuous outcome scales will be a 2-group (treatment) mixed general linear model of timepoints nested within participants. This is very general linear model that permits flexibility in specifying the nature of the covariances among the dependent measures, allows time-dependent, within and between subject covariates, and permits incomplete (i.e., missing) data. Analyses of trends across the monthly assessments will be done using growth curve model within the mixed model analysis of covariance design with repeated measures described above. We propose to model a linear trend of time unless inspection clearly suggests nonlinearity. By fitting a slope over time (and intercept) for each participant who has baseline and at least one other measure, this method makes good use of all the data, and is robust even if some of the some measures are missing. The use of the mixed general linear model for all cross-sectional and linear hypotheses ensures that results will be comparable across different analyses and provide a framework to include group, person and time-specific covariates if it becomes necessary. The preliminary analyses have shown that this analysis strategy provides meaningful results even with partial data and suggests that we will exceed the originally projected power.**4. Stratification:** Randomization will be stratified by type of antipsychotic and presence of mood stabilizer medication (e.g., depakote, lithium) to assure balance on olanzapine and clozapine by randomizing within three strata – olanzapine, clozapine, and all other antipsychotics -- using three separate randomization lists. Because such stratification can adversely affect statistical power by creating artificially comparable (and heterogeneous) groups, two dummy variables coding olanzapine and clozapine at baseline will be included in all analyses as covariates.

4. Statistical Plans:

Primary Hypotheses:

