Analysis plan: We do not expect to see meaningful weight loss in the usual care group, and thus do not expect meaningful correlations based on these hypotheses. Accordingly, the primary tests of each of these hypotheses will be done by computing Pearson correlations between the specified variables within the treatment group. Supplementary analyses will be done within the context of the mixed effects designs described above, including these variables as possible treatment effect moderators. Separate analyses for hypotheses (i.) through (iv.) above will be done to examine possible interactions of each of these variables considered separately with treatment group. These analyses will test whether treatment may be more or less effective as a function of these variables (negative symptoms, motivation to change, cognitive cluster, insight). If so, we will stratify the groups according to these variables to simplify presentation of the results, e.g., treatment outcomes presented separately in groups with more versus less cognitive impairment).

b) SMI patients involved in the Lifestyle Balance Program will have better adherence to psychiatric treatment than the Usual Care group as measured by percent of psychotropic medication refills and percent of appointments attended.

Analysis plan: We will compute these dependent measures (percent of psychotropic medication refills and percent of appointments attended) to create summary scores within each of the three study follow-up epochs (baseline- 8 weeks, 8 weeks- 6 months, 6-12 months). These will be analyzed using general linear mixed effects models with repeated measures, including baseline stratification medication as a covariate. We will test group, time and interaction effects, and perform between-group contrasts for each time period.

To determine what patient characteristics, e.g. Medication group, diagnostic or symptom status is most conducive to positive outcome we will use classification analysis using the recursive partitioning algorithm to determine which patient characteristics at baseline are the best predictors for positive outcomes. Recursive partitioning is a computationally intense data mining technique that allows for the analysis of multiple predictors simultaneously while protecting against type I error inflation due to multiple testing and it provides non-parametric confidence intervals by using cross-validation (75).

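### The primary tests of secondary hypothesis (a) are unadjusted Pearson correlations, although the plan requires the olanzapine and clozapine dummies in all analyses; part of any correlation could therefore reflect drug group.

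*Combined protocol and SAP*

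**What the plan says.** Section V.N, Stratification, sets up three randomisation strata (olanzapine, clozapine, all other antipsychotics) and adds that "two dummy variables coding olanzapine and clozapine at baseline will be included in all analyses as covariates". The reason given concerns power: "Because such stratification can adversely affect statistical power by creating artificially comparable (and heterogeneous) groups".

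Section V.N, Statistical Plans, secondary hypothesis (a), covers negative symptoms, motivation, cognitive impairment and insight as correlates of weight loss. Its analysis plan says that "the primary tests of each of these hypotheses will be done by computing Pearson correlations between the specified variables within the treatment group", and it names no covariate. Mixed models with these variables as treatment-effect moderators are supplementary. The analysis plan for hypothesis (b), directly after it, does name the covariate: "including baseline stratification medication as a covariate".

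Three other places bear on clozapine:
- Section II.D: "Indeed, CLOZ is reserved for the most refractory patients".
- Section II.E, on an earlier chart review of simple behavioral measures: "these strategies seemed to have little effect in CLOZ treated subjects".
- Section IV.E.2.g, on preliminary data from the previous trial: "the weight gain in patients on clozapine and risperidone does not appear to respond to the training program". The same paragraph calls these results very preliminary because the subgroups are small.

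**The concern.** The two instructions cannot both be followed as written. An analyst who follows the hypothesis (a) text leaves out the covariates that the Stratification paragraph requires.

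The omission could change the answer. These tests compare patients within one arm by their symptom level, which is not randomised, so randomisation does not balance drug group across symptom levels. If clozapine patients lose less weight and also score worse on the predictor, the two appear correlated, in the hypothesised direction, even where they are unrelated among patients on the same drug. The trial could then report that negative symptoms, cognitive impairment or poor insight hinder weight loss when part of the pattern is drug group. Section I.B lists medication and psychosocial status as separate characteristics by which to identify the veterans most likely to benefit, and an unadjusted correlation cannot separate the two.

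**Working it through.** **Text.** Setting the passages side by side is enough to show the inconsistency: covariates in all analyses (Stratification), a covariate-free primary test (hypothesis (a)), and the covariate named again (hypothesis (b)). No simulation is needed for this.

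**Inputs for the size.**
- From section V.N.5: N = 120, 45% attrition, 66 completers, two-sided alpha 0.05, SD of weight loss about 5 kg (11 lb). The section gives no power or precision for the correlations. Its between-group figure does reproduce: lambda = 0.25² × 66 × 4 / (1 + 3 × 0.5) = 6.6 on 1 and 64 df gives 0.716, against the stated 0.7199.
- Assumed: 1:1 allocation, which the plan does not state. The program arm then has n = 33 completers, or 60 if every randomised patient contributes.
- Assumed, because the documents give neither: clozapine share p = 0.1 to 0.3, and a predictor dx = 0.5 to 1.0 SD worse on clozapine.
- Assumed weight-loss deficit on clozapine: dy = 6.6/11 = 0.60 to 11.8/11 = 1.07 SD. The numerators are the preliminary program-arm loss and group difference in section IV.E.2.a.

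**Formula.** With no association within drug groups and v = p(1 − p), the correlation produced by clozapine alone is

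r = −v·dx·dy / √[(1 + v·dx²)(1 + v·dy²)].

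The rejection rate is approximately Φ(z − 1.96) + Φ(−z − 1.96), where z = atanh(|r|)·√(n − 3).

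**Middle case** (p = 0.2, dx = 1, dy = 1.07). Here v = 0.16, so r = −0.171/√(1.16 × 1.183) = −0.146. At n = 33, z = 0.147 × √30 = 0.81 and the rate is 13%. At n = 60, z = 0.147 × √57 = 1.11 and the rate is 20%.

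| Weight-change SD | p | dx | dy | r | n = 33 | n = 60 |
|---|---|---|---|---|---|---|
| 11 lb | 0.1 | 0.5 | 0.60 | −0.03 | 5% | 6% |
| 11 lb | 0.2 | 1.0 | 1.07 | −0.15 | 13% | 20% |
| 11 lb | 0.3 | 1.0 | 1.07 | −0.18 | 17% | 29% |
| 16.5 lb | 0.2 | 1.0 | 0.715 | −0.10 | 9% | 12% |
| 16.5 lb | 0.3 | 1.0 | 0.715 | −0.13 | 11% | 17% |

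Simulation agrees with these rates to within about a percentage point.

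**Why 16.5 lb.** Section IV.E.2.a gives a six-month range in the program arm from a 50 lb loss to a 14 lb gain, a span of 64 lb. If the 46 participants split evenly (assumed), the expected range of 23 normal values is about 3.85 SD, and 64/3.85 is about 16.6 lb. The same pound differences are then fewer SDs: 11.8/16.5 = 0.715.

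**After adjustment.** The partial correlation given the two dummies rejects at about 5% in every simulated case where clozapine and olanzapine are the only drug differences.

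**Cost.** The critical |r| is t/√(t² + df). At n = 33 it moves from 0.344 (31 df) to 0.355 (29 df), and power at r = 0.4 from 0.64 to 0.61. At n = 60 it moves from 0.254 to 0.259, and power from 0.89 to 0.88.

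**The case against.** **The plan already has adjusted analyses.** The supplementary mixed models would carry the dummies under the Stratification rule, and the recursive partitioning takes medication group and symptom status together. That stands, and it limits the damage. But neither is the primary test, and if they disagreed with the Pearson result the plan would give priority to the unadjusted one.

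**The covariate rule was written for power, not confounding.** True. The confounding argument is an inference from sections II.D, II.E and IV.E.2.g. The rule still says all analyses.

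**The hypotheses are worded mostly as correlations.** If clozapine patients have worse symptoms and lose less weight, the marginal correlation is real. Clozapine may also mark severity, so that conditioning on it removes part of a true severity effect. This is a fair point, and it is why both correlations should be reported. The heading of the hypothesis, however, speaks of symptoms affecting weight loss.

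**Two dummies may not be enough.** Section IV.E.2.g reports that risperidone patients also did not respond, and they fall in the stratum of all other antipsychotics. If 25% of patients took risperidone with the same 1.07 SD deficit, and their predictor scores were also 0.5 to 1.0 SD worse (all assumed), the adjusted test would still reject in up to about 12% of trials at n = 33 and 18% at n = 60. This stands as a limit on the fix.

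**Stronger readings.** A reader might infer that the drug is the true driver. The documents do not show this: section II.D says nothing about negative symptoms, cognition or insight on treatment, and the early drug data cannot separate drug from severity. A reader might also infer that using one arm is itself an error, since pilot weight change ran "from a loss of 19 pounds to a gain of 29 for the usual care group" and correlation depends on spread, not on the mean. The point about spread is correct, but the supplementary models already test interactions with treatment group, so a two-arm primary model is a preference. Adjustment for baseline weight is likewise a preference; no rule in the plan calls for it.

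**Conclusion.** The concern holds in limited form. The plan contradicts itself on whether the primary tests of hypothesis (a) are adjusted for drug group, and the text as written leaves out a factor that its own early data tie to weight response.

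The size is conditional. Without any within-drug association, the 5% test rejects in about 5 to 17% of trials at n = 33 and 6 to 29% at n = 60 with the plan's 11 lb SD. With an SD of 16.5 lb the upper ends are about 11% and 17%. The low end is negligible. The figures rest on an assumed clozapine share, an assumed symptom gap that the documents do not report, weight-response data that the plan calls very preliminary, and 1:1 allocation. The n = 60 figures also require outcome data on every program patient, against 45% expected attrition. The supportable claim is that drug group can pass for a symptom effect, not that it will.

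This concerns a secondary hypothesis only. The randomised treatment comparison is untouched.

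**What to change.** In the analysis plan for secondary hypothesis (a), make the primary test of each part a partial correlation, or the equivalent regression, of weight loss on the predictor within the program arm, adjusted for the olanzapine and clozapine dummies. Report the unadjusted Pearson correlation beside it, so that readers can see how much of the association runs through drug group. Leave the supplementary mixed models and the recursive partitioning as planned.

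The change is to wording only, since baseline antipsychotic is already recorded for stratification. It costs two degrees of freedom per test, with the small loss of power shown above. The write-up should say that differences among drugs within the stratum of all other antipsychotics, risperidone for example, may still confound the result.

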Prior to statistical analyses, the data will be inspected to determine the advisability of scale transformation to normalize distributions or reduce variance heterogeneity (e.g., logarithmic or power transformations) and to identify missing data, outliers, or other unusual features that might bias results. Where multiple measures may overlap or be redundant, preliminary analyses will explore whether it is possible to reduce these using techniques from scale development such as factor analyses. Preliminary analyses are also performed to compare treatment groups on descriptive and clinical characteristics at baseline to ensure randomization has succeeded. If there are significant differences between the treatment groups at baseline we will create propensity scores and include them in all further analyses as covariates to compensate for potential bias. We will also test if there are significant site effects, and if necessary we will include a site variable in the mixed linear model analysis, and model time as nested in subjects and subjects nested in sites.

To address concerns about excessive Type I error rates, the principal analyses are designed to answer clearly stated major research hypotheses, and are based on well-specified dependent variables. The samples are large enough to expect that confidence limits may be reasonably narrow, and findings may be robust enough to permit conservative adjustments of p-values for multiple testing. Bonferroni and other adjustments are necessarily somewhat arbitrary as Saville notes in his argument against their use (71). Additional analyses that are exploratory will be clearly identified as such. All tests will be two-tailed at $\alpha=0.05$.

2. Attrition: Dropout from treatment does not necessarily mean participants will refuse follow-up assessments, and we will attempt to obtain full follow-up data on all enrolled participants regardless of degree of participation and include all enrolled participants in analyses when any outcome data are available (intent to treat). Attrition can compromise randomization, so preliminary analyses will compare baseline characteristics

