General linear mixed effects models permit missing data but assume that data are missing at random. We will explore this assumption by comparing attrition rates in the study groups, and by comparing patients with and without post-treatment data on baseline scores and other baseline characteristics. If missing at randomness does not seem like a valid approach we will use multiple imputation based on different models of missingness to determine the degree of potential bias due to the way we approach the problem of missing data. Based on our experience with similar data we don't expect the data to violate missingness at random, but if it does we will use the results of the multiple imputation based on the EM algorithm to derive confidence intervals for our parameter estimates.

For Primary Hypothesis C, intraclass correlations will be run to assess the concurrent validity of the BPSS (compared to the WHO-QOL) to examine the relationship between study participation and biopsychosocialspiritual wellness.

Secondary Hypotheses:

a) Negative and Cognitive Symptoms will affect weight loss. Specifically we hypothesize: i.) High levels of negative symptoms as rated by the BPRS negative symptom cluster will correlate negatively with weight loss; ii.) Motivation to change level will impact weight loss directly; iii.) High levels of cognitive impairment as measured by the BPRS cognitive cluster will correlate with low weight loss, and; iv.) Insight into illness (as measured by the SAIQ) will correlate directly with weight loss. v.) High motivation as measured by the URICA will correlate with successful weight loss

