It provides valid statistics even in cases where there are more potential predictors than observations, and allows us to include all demographic, psychosocial, psychiatric and medical data known at baseline as potential predictors. The results of this analysis will suggest which patients are most likely to profit from further interventions, and it will also characterize the most at risk patients.

c) Subjects will continue to give meaningful, informed consent to participate throughout the study. They will see no significant decrease in their score on the informed consent quiz given every 6 months.

Analysis plan: A general linear model (GLM): ANOVA will be performed to compare the informed quizzes score results at 0, 6, and 12 months during the subjects' participation in the study.

5. Power Analysis: All calculations are based assuming a conventional medium effect size ($f=.25$, Cohen 1988); and a two-tailed alpha set at 0.05. Tuomilehto et al. estimated the SD of weight loss at roughly 5 kg across several treatment conditions (lifestyle changes vs. control) (76). A medium effect would thus translate into a group difference of about 2.5 kg or about 5.5 pounds. With an enrollment of $N=120$ and an estimated attrition rate of 45% we expect that at least 66 subjects will provide complete the study and provide 4 data points. The power analyses below are based on a sample size of $N=66$, i.e. this is a very conservative estimate due to the fact that the mixed linear model allows us to include cases with missing values in the analyses and that while they don't provide as much information as complete cases they still provide some information and will increase power. For the between-group comparisons, $N=66$ yields power=.7199 for main differences between groups if we assume that the within subject correlation is $r=.50$. Power to test for the difference in outcome trajectories of time – our main outcome variable is 0.99, and even if the effect is as small as $f=0.15$ we will have sufficient power to distinguish between the trajectories of the two treatment groups (power=0.83) insuring that we will get significant, insuring that we Preliminary data analyses shows that these assumptions are quite conservative and that effect sizes seem to be slightly larger than projected, suggesting that the final power will exceed the estimates presented here.

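### Subgroup outcomes will be shown only for moderators whose interaction looks positive, with no threshold or cut-point fixed; showing all four from the continuous model would be better and cheap

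*Combined protocol and SAP*

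**What the plan says.** Section V.N, Statistical Plans, Secondary Hypotheses (a), sets out two layers of analysis. The primary tests of the hypothesis are Pearson correlations with weight loss, computed in the Lifestyle Balance arm only. Moderator analyses in the mixed model follow and are called supplementary: "Separate analyses for hypotheses (i.) through (iv.) above will be done to examine possible interactions of each of these variables considered separately with treatment group". The four variables are negative symptoms, motivation to change, the BPRS cognitive cluster and insight. If treatment works better or worse according to one of them, the plan continues: "If so, we will stratify the groups according to these variables to simplify presentation of the results". Its example is outcomes shown separately for patients with more and with less cognitive impairment. It does not say how more and less are divided.

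The general rules are in V.N.1, General Data Analysis Issues. They state "All tests will be two-tailed at" 0.05. On multiplicity they say that "findings may be robust enough to permit conservative adjustments of p-values for multiple testing", then that "Bonferroni and other adjustments are necessarily somewhat arbitrary". No method or family is named. They also promise that "Additional analyses that are exploratory will be clearly identified as such".

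Motivation appears twice in the list of sub-hypotheses, as (ii) and again as "v.) High motivation as measured by the URICA will correlate with successful weight loss". Section I.D.2(a) names the URICA as the motivation measure. The interaction analyses stop at (iv).

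**The concern.** The rule makes the display depend on the result. A variable with a positive interaction gets a split-group presentation, and the others get none. Estimates shown only because they passed a test are too large on average. Cutting a continuous score in two makes a gradient look like a step, and leaving the cut open adds discretion at the point where the data have already been seen.

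Learning which veterans benefit most is one of the short-term objectives (Section I.B). A chance split on, say, cognitive impairment could therefore be read as guidance on whom to refer to the programme when it is rolled out to other sites.

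**Working it through.** **Inputs from the documents.** Two-sided alpha 0.05 (V.N.1, repeated in V.N.5); four interaction tests (V.N, Secondary Hypotheses (a)); 120 enrolled, 45% attrition, SD of weight loss about 5 kg, medium effect about 2.5 kg (V.N.5).

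**Assumptions.** 1:1 allocation, so 120 × 0.55 / 2 = 33 completers or 120 / 2 = 60 enrolled per arm. Correlation among the four variables from 0 to 0.8, since the documents give none. An interaction counts as positive at unadjusted p < 0.05. Weight change is treated as one outcome per patient in a linear model.

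**The plan's own figure.** No error rate or power is stated for this hypothesis. The power section's between-group figure can be reproduced: λ = 0.25² × 66 × 4 / (1 + 3 × 0.5) = 16.5 / 2.5 = 6.6, with 1 and 64 df, gives power 0.716 against the stated 0.7199. The sample-size inputs are therefore being read as intended.

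**Chance of at least one false split.** For four independent tests: 1 − 0.95⁴ = 18.5%. The expected number of false interactions is 4 × 0.05 = 0.2. Simulation with no moderation by any variable (4,000 to 6,000 trials per setting):

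| Correlation among variables | 33 per arm | 60 per arm |
|---|---|---|
| 0 | 19% | 19% |
| 0.3 | 17% | 18% |
| 0.5 | 15% | 16% |
| 0.6 | 15% | 15% |
| 0.8 | 11% | 11% |

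Allowing for simulation error, the range is about 11-20%. Sample size hardly matters, because this is a type I error rate.

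**Size of the false gap.** Every simulated patient was given the same 2.5 kg effect with SD 5 kg, and the rule was followed with a median split (assumed). When a chance interaction triggered the split, the median absolute difference between the two subgroup effects was about 4.5 kg at 33 per arm and about 3.3-3.4 kg at 60 per arm.

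A hand check agrees. With four cells of n/2 patients, the standard error of the difference between subgroup effects is 5 × √(4 / (n/2)). That is 5 × √(4/16.5) = 2.46 kg at n = 33 and 5 × √(4/30) = 1.83 kg at n = 60. A gap that accompanies p < 0.05 must be near two standard errors: 1.96 × 2.46 = 4.8 kg and 1.96 × 1.83 = 3.6 kg. The simulated medians are a little lower because the test uses the continuous score and the display uses the split. Relative to the planned effect, the false gap is 4.5 / 2.5 = 1.8 times and 3.3 / 2.5 = 1.3 times as large.

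**The case against.** The plan has real safeguards. The four variables are named in advance and the correlations have stated directions. Strata follow an interaction test, which is sounder than testing within subgroups. The split is described as presentation, and no within-stratum tests are planned. The moderator analyses are ranked below the correlations as supplementary, and V.N.1 has a general rule for labelling exploratory work. The objective of finding who benefits also has its own analysis, recursive partitioning with cross-validation, for which the plan claims protection against type I inflation.

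All of this stands, and it rules out several stronger readings that a reader might infer:

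- **That chance subgroups will be presented as findings.** If nothing moderates the effect, about 80-89% of trials would show no split.
- **That the tests have no hierarchy.** The plan separates primary from supplementary tests.
- **That the relevant error is the 24-30% simulated (correlation 0.6 down to 0) for at least one positive among all eight tests.** The correlations trigger no split, so the family for this harm is the four interactions.
- **That the plan sets a 0.05 trigger.** It says only that stratification follows if the effect varies; 0.05 is inferred from the general rule.
- **That the correlations must be adjusted.** Whether four pre-named secondary hypotheses need family-wise control is debatable. At 33 in the programme arm, testing at 0.0125 would cut power for r = 0.4 from 64% to 43%.

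The safeguards do not reach the selection itself. Supplementary is not the same as exploratory, and the moderator section does not apply the exploratory label. Neither label would change which variables are displayed or where the cut falls.

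**Conclusion.** The concern holds as a reporting weakness in a secondary analysis. The conditional rule would show a split due to chance in about 11-20% of trials with no true moderation, typically with a subgroup gap larger than the whole planned treatment effect. The rate rests on reading the trigger as unadjusted p < 0.05 and on the assumed correlations. The gap rests also on the median split and on the plan's 2.5 kg and 5 kg. The primary comparison and the validity of each interaction test are untouched. The double listing of motivation is a wording point: it leaves open whether there are four or five correlations, but adds no interaction and no split.

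**What to change.** Remove the conditional stratification rule. For each of the four variables, whether or not its interaction is significant, report the interaction estimate and the treatment effect with 95% confidence interval from the continuous interaction model, evaluated at the 25th and 75th percentiles of the pooled baseline distribution. Label the four analyses exploratory in the moderator section itself. This removes the selection and the open cut-point together.

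The cost is a few lines of SAP text and one extra table from models already planned. The display is slightly less simple than two subgroups.

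As an editorial change, merge (ii) and (v) into one motivation test using the URICA. A Holm adjustment of the four correlations is optional and not part of this fix.
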